6.3.1.1 Bisphosphonates and denosumab

Bisphosphonates and denosumab are generally allowed with the following comments:

- Chronic concomitant bisphosphonate/denosumab therapy for the prevention of bone metastasis is not permitted.

- Bisphosphonate/denosumab therapy for the treatment of osteoporosis is permitted.
- Bisphosphonate/denosumab therapy for the prevention of skeletal related events for patients with bone metastases is permitted.

Patients taking concomitant medication chronically should be maintained on the same dose and dose schedule throughout the study period, as medically feasible.

6.3.1.2 Corticosteroids

Chronic dosing of corticosteroids such as dexamethasone and prednisone is known to lead to induction of CYP3A enzymes, thereby potentially increasing the risk of reducing ribociclib drug exposure to subtherapeutic levels. Systemic corticosteroid treatment should not be given during the study, except for:

- Topical applications (e.g., rash), inhaled sprays (e.g., obstructive airways diseases), eye drops or local injections (e.g., intra-articular). A short duration (< 5 days) of systemic corticosteroids \leq to the anti-inflammatory potency of 4 mg dexamethasone (e.g. for chronic obstructive pulmonary disease, or as an antiemetic) will be accepted.

6.3.1.3 Hematopoietic growth factors

Hematopoietic growth factors may be used according to ASCO guidelines (Smith 2006).

6.3.1.4 Palliative radiotherapy

Palliative radiation is permitted. It should not be delivered to a target lesion and it should not encompass more than 25% of irradiated bone marrow. Palliative radiated lesions cannot be considered for evaluation of tumor response.

If palliative radiotherapy is initiated after the start of study treatment, the reason for its use must be clearly documented and progression as per RECIST 1.1 must be ruled out.

No dose modification of study treatment is needed during palliative radiotherapy.

Refer to the ribociclib Investigators Brochure and letrozole or goserelin acetate package insert and [Appendix 14.1](#). for information on possible interactions with other drugs.

6.3.2 Permitted concomitant therapy requiring caution and/or action

Medications to be used with caution during combined ribociclib and letrozole treatment in this study are listed below (see [Table 14-2](#) in [Appendix 14.1](#), this list is not comprehensive and is only meant to be used as a guide. Please contact the medical monitor with any questions). These medications should be excluded from patient use if possible. If they must be given based on the investigator's judgment, then use with caution and consider a ribociclib interruption if the concomitant medication is only needed for a short time.

- Moderate inhibitors or inducers of CYP3A4/5
- Sensitive substrates of CYP3A4/5 that do not have narrow therapeutic index
- Inhibitors of BSEP (based on in vitro data co-administration with LEE011 may lead to intrahepatic cholestasis)
- Medications that carry a possible risk for QT prolongation

- Sensitive substrates of the renal transporters MATE1/2 and OCT1/2 (potential to increase exposure to substrates of these transporters, although no animal or clinical data are available to support these statements)
- Sensitive substrates of BCRP (potential to increase exposure to substrates of these transporters, although no animal or clinical data are available to support these statements))
- Substrates metabolized predominantly by CYP2C19 or CYP2A6 with a narrow therapeutic index (that could be affected by letrozole)

6.3.3 Prohibited concomitant therapy

The following medications are prohibited during study treatment in the study (see [Table 14-1](#) in [Appendix 14.1](#), this list is not comprehensive and is only meant to be used as a guide. Please contact the medical monitor with any questions):

- Strong inhibitors or inducers of CYP3A4/5
- Substrates of CYP3A4/5 with a narrow therapeutic index
- Medications with a known risk for QT prolongation and/or TdP
- Other investigational and antineoplastic therapies
- Herbal preparations/medications and dietary supplements that are strong inhibitors or inducers of CYP3A4/5 or those with a known risk of QT prolongation. These include but are not limited to: St. John's wort, Kava, ephedra (ma huang), gingko biloba, dehydroepiandrosterone (DHEA), yohimbe, saw palmetto and ginseng. Patients should stop using these preparations/medications at least 7 days prior to first dose of study treatment.

6.3.4 Drugs with QT prolongation

As far as possible, avoid co-administering medications with a “Known”, “Possible” or “Conditional” risk of TdP ([qtdrugs.org](#)) or any other medication with the potential to increase the risk of drug-related QT prolongation (e.g. via a potential DDI increasing the exposure of LEE011/ placebo or the exposure of the QT prolonging drug). If concomitant administration of drugs with a known risk of TdP is required and cannot be avoided, LEE011/placebo must be interrupted. If during the course of the study, concomitant administration of a drug with “Possible risk” or “Conditional risk” of TdP is required, based on the investigator assessment and clinical need, study treatment may be resumed under close clinical and ECG monitoring to ensure patient safety. A list of drugs associated with QT prolongation and/or TdP is available online ([www.qtdrugs.org](#)). Medications with a known risk for QT prolongation are prohibited during study treatment.

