1.2.1.2.1 Clinical safety of ribociclib as single agent

As of 15-Jun-2015, 157 patients have been treated with single agent ribociclib in the first-in-human (FIH) phase I study; 85 patients have been treated in the initial dose escalation part for the 3 week on/1 week off regimen and 47 patients in the dose expansion part of the study; 18 patients were enrolled for the continuous dosing regimen with ribociclib and, 7 patients were enrolled in the liquid formulation cohort.

Patients with advanced solid tumors or lymphomas were treated with increasing doses of ribociclib orally, once daily (qd) for 21 days followed by a 1-week rest (28-day cycle). Doses ranging from 50 mg to 1200 mg were evaluated on this schedule. Treatment has been discontinued in 120 (90%) patients; the primary reasons for treatment discontinuation were: disease progression (106 [80%] patients); adverse events (AEs) (7 [5%] patients); death (2 [1.5%] patients); withdrawal of consent (3 [2%] patient); and loss to follow up (1 [1%] patient).

The most frequently reported AEs ($\geq 10\%$), regardless of grade, causality and ribociclib dose were: nausea (52.3%); fatigue (40.9%); diarrhea (37.1%); vomiting (35.6%); neutropenia (34.1%); anemia (32.6%); decreased appetite, thrombocytopenia (23.5% each); white blood cell count decrease (22.7%); leukopenia (22%); constipation (21.2%); dyspnea (20.5%); asthenia (19.7%); cough (18.2%); hyperglycemia (17.4%); headache, hypoalbuminemia (16.7% each); ECG QT prolonged (15.9%); abdominal pain, back pain, lymphocyte count decrease, pyrexia (15.2% each); AST increase, blood creatinine increased, dizziness, lymphopenia (14.4% each); peripheral edema (13.6%); neutrophil count decreased (12.9%); ALT increase, pain in extremity (12.1% each) and hypocalcemia (11.4%).

For either continuous or intermittent dosing, the onset of neutropenia (most frequently Grade 2) occurs by Day 15, reaching a nadir in the third or fourth week with recovery during the week of drug holiday for the three weeks on/one week off schedule. Some patients require additional time for recovery (7 to 14 days). QT changes become evident in the first cycle by Day 8 and later (once steady state is reached), are associated with the maximum drug levels between 1 to 8 h post-dose, and remain stable or improve in subsequent cycles.

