1.2.1.2.3 Clinical pharmacokinetics of ribociclib

As of 15-Jun-2015, preliminary PK data were available from approximately 143 patients from the first-in-human (FIH) study [CLEE011X2101] across the dose range of 50 to 1200 mg. Following oral dosing, ribociclib was rapidly absorbed with median T_{max} ranging from 1 to 4 hours. Ribociclib plasma exposure (C_{max} and AUC_{0-24h}) exhibited slightly over-proportional increases in exposure across the dose range tested. Steady-state was generally reached by Day 8 and the mean effective $T_{1/2}$ based on accumulation ratio (i.e., $T_{1/2, acc}$) ranged from 12.3 to 42.9. The mean accumulation ratio (R_{acc}) calculated from AUC_{0-24h} at steady-state and AUC_{0-24h} after a single dose across the studied doses ranged from 1.35 to 3.11.

At the recommended dose for future development (600 mg), steady-state plasma C_{max} ($n=56$) ranges from 606-6170 ng/mL (geometric mean = 1790 ng/mL or 4.1 μ M), median T_{max} ($n=72$) is 2.1 h, and AUC_{0-24h} ($n=53$) ranges from 6770-90600 ng* h /mL (geometric mean = 23600 h*ng/mL). At this dose, inter-patient variability in C_{max} and AUC is 62% and 66%, respectively, as assessed by geometric coefficient of variation (CV%). At the 600 mg dose level, LEQ803, an active metabolite of ribociclib, accounted for approximately 8% (geometric mean) of ribociclib AUC_{0-24h} after single and multiple doses. Refer to the ribociclib [Investigators Brochure] for more details.

In a food effect study [CLEE011A2111] in 24 healthy subjects, a single dose of ribociclib (600 mg) was administered as drug-in-capsule (DiC) with a high-fat, high-calorie meal and under fasted conditions. Compared to the fasted state, oral administration of a single 600 mg dose of ribociclib DiC with a high-fat, high-calorie meal decreased the rate of absorption of ribociclib resulting in a 23% decrease in C_{max} (geometric mean ratio: 0.775; 90% confidence interval [CI]: 0.700, 0.858) and a median difference in T_{max} of 2 hours. However, there was no effect on the extent of absorption of ribociclib as the overall exposure (AUC_{inf}) was unaffected under fed conditions (geometric mean ratio: 0.994; 90% CI: 0.925, 1.070). A similar trend was observed for LEQ803, an active metabolite of ribociclib, with a decrease in C_{max} (32%), a delay in median T_{max} , and no substantial effect on overall exposure. Based on these data, ribociclib DiC can be taken without regard to meals.

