	All Grades n (%)	Grade 3/4 n (%)	All Grades n (%)	Grade 3/4 n (%)	All Grades n (%)	Grade 3/4 n (%)
Neutropenia	13 (68)	7 (37)	20 (71)	13 (46)	33 (70)	20 (43)
Nausea	7 (37)	0	13 (46)	0	20 (43)	0
Fatigue	7 (37)	0	5 (18)	0	12 (26)	0
Alopecia	0	0	11 (39)	0	11 (23)	0
Anemia	4 (21)	0	7 (25)	0	11 (23)	0
Diarrhea	3 (16)	0	8 (29)	0	11 (23)	0

Asthenia	0	0	10 (36)	0	10 (21)	0
Neutrophil count decreased	3 (16)	2 (11)	5 (18)	3 (11)	8 (17)	5 (11)
ALT increased	1 (5)	1 (5)	6 (21)	1(4)	7 (15)	2 (4)
AST increased	1 (5)	1 (5)	6 (21)	0	7 (15)	1 (2)
Dry skin	0	0	7 (25)	0	7 (15)	0
Headache	2 (11)	0	5 (18)	0	7 (15)	0
Pruritus	0	0	7 (25)	0	7 (15)	0
Vomiting	1 (5)	0	6 (21)	0	7 (15)	0

The median relative dose intensity of ribociclib was >98% in both groups. AEs suspected to be study drug-related (all Grade $\geq 15\%$ in all pts) are summarized in [Table 1-2](#). The most common (>30% of pts) all-Grade AEs were neutropenia (33 pts [70%]) and nausea (20 pts [43%]). The most common (>5% of pts) Grade 3/4 AEs suspected to be drug-related were: neutropenia (20 pts [43%]), neutrophil count decreased (5 pts [11%]), and white blood cell count decreased (3 pts [6%]). PK data collected from patients in [CLEE011X2107] are summarized in [Table 1-3](#). Ribociclib exposure (C_{max} and AUC_{0-24h} ; [Table 1-3](#)) in combination with letrozole was consistent with ribociclib single-agent data, indicating no PK drug–drug interaction. Ribociclib accumulated 2.4-fold following multiple doses, possibly due to a combined effect of drug accumulation and auto-inhibition of CYP3A4. Letrozole exposure (C_{max} and AUC_{0-24h} ; Table 1-3) on C1D21 was similar to or slightly lower than previously reported in studies with letrozole. Variability in attainment of steady-state for letrozole (2–6 weeks) could account for differences. Letrozole accumulation was 5.2-fold following multiple doses, consistent with the long half-life reported for letrozole (≈ 2 days).

Table 1-3 PK Parameters of ribociclib and letrozole in all patients (N=47)

Analyte	Day	T_{max} (h)*	C_{max} (ng/mL)†	AUC_{0-24} (h.ng/mL)†	R_{acc} †	$T_{1/2, acc}$ (h)†	CL/F (L/h)†
Ribociclib	C1D1	2.1 (1.0-4.2) [41]	1130 \pm 486 [41]	10900 \pm 3750 [37]	-	-	-
	C1D21	2.1 (1.0-7.7) [28]	1870 \pm 750 [28]	25900 \pm 11600 [23]	2.4 \pm 0.8 [19]	32.5 \pm 12.5 [18]	30.1 \pm 17 [20]
Letrozole	C1D1	2.0 (0.5-8.0) [42]	25.7 \pm 13 [42]	378 \pm 297 [38]	-	-	-

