13. Patient has impairment of gastrointestinal (GI) function or GI disease that may significantly alter the absorption of the study drugs (e.g., ulcerative diseases, uncontrolled nausea, vomiting, diarrhea, malabsorption syndrome, or small bowel resection)
14. Patient has a known history of HIV infection (testing not mandatory).
15. Patient has any other concurrent severe and/or uncontrolled medical condition that would, in the investigator's judgment, cause unacceptable safety risks,

contraindicate patient participation in the clinical study or compromise compliance with the protocol: (e.g. chronic pancreatitis, chronic active hepatitis, active untreated or uncontrolled fungal, bacterial or viral infections, etc.).

16. Clinically significant, uncontrolled heart disease and/or cardiac repolarization abnormality, including any of the following:
 - History of acute coronary syndromes (including myocardial infarction, unstable angina, coronary artery bypass grafting, coronary angioplasty, or stenting) or symptomatic pericarditis within 6 months prior to screening.
 - History of documented congestive heart failure (New York Heart Association functional classification III-IV).
 - Documented cardiomyopathy.
 - Clinically significant cardiac arrhythmias (e.g. ventricular tachycardia), complete left bundle branch block, high-grade AV block (e.g. bifascicular block, Mobitz type II and third-degree AV block).
 - Long QT syndrome or family history of idiopathic sudden death or congenital long QT syndrome, or any of the following:
 - Risk factors for Torsades de Pointe (TdP) including uncorrected hypokalemia or hypomagnesemia, history of cardiac failure, or history of clinically significant/symptomatic bradycardia.
 - Concomitant use of medication(s) with a known risk to prolong the QT interval and/or known to cause Torsades de Pointe that cannot be discontinued (within 5 half-lives or 7 days prior to starting study drug) or replaced by safe alternative medication.
 - Inability to determine the QT interval on screening (QTcF, using Fridericia's correction).
 - Systolic blood pressure (SBP) >160 mmHg or <90 mmHg at screening.
17. Patient is currently receiving any of the following substances and cannot be discontinued 7 days prior to Cycle 1 Day 1:
 - Known strong inducers or inhibitors of CYP3A4/5, including grapefruit, grapefruit hybrids, pomelos, star-fruit, and Seville oranges.

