6.2.1.3 Additional follow-up for QTc prolongation

Table 6-5 Ribociclib dose adjustment and management recommendation for QTc prolongation (CTC AE v4.03)

Grade	Dose Modification
For All Grades	
1. Check the quality of the ECG and the QT value and repeat if needed.2. Perform analysis of serum electrolytes (K+, Ca++, Phos, Mg++). If outside of the normal range, interrupt ribociclib administration, correct with supplements or appropriate therapy as soon as possible, and repeat electrolytes until documented as normal.3. Review concomitant medication usage for the potential to inhibit CYP3A4 and/or to prolong the QT interval.4. Check compliance with correct dose and administration of ribociclib. 
Consider collecting a time matched PK sample; record date and time of last study drug intake.

1 QTcF 450-480 ms	Perform steps 1-4 as directed in "For All Grades". No dose adjustment required.
2 QTcF 481-500 ms	
Interrupt ribociclib. Perform steps 1-4 as directed in "For All Grades."
 
Perform a repeat ECG within one hour of the first QTcF of ≥ 481 ms. Repeat ECG as clinically indicated until the QTcF returns to < 481 ms, restart LEE011 with dose reduced by 1 dose level.
 
If QTcF ≥ 481 ms recurs, ribociclib should be reduced by 1 dose level. Repeat ECGs 7 days and 14 days after dose resumption (then as clinically indicated) for any patients who had therapy interrupted due to QTcF ≥ 481 ms.

3 QTcF ≥ 501 ms on at least two separate ECGs	
Interrupt ribociclib. Perform steps 1-4 as directed in "For All Grades."
 
Transmit ECG immediately and confirm prolongation/abnormalities.
 
Perform a repeat ECG within one hour of the first QTcF of ≥ 501 ms.
 
If QTcF remains ≥ 501 ms, consult with a cardiologist (or qualified specialist) and repeat cardiac monitoring as indicated until the QTcF returns to < 481 ms.
 
If QTcF returns to < 481 ms, ribociclib will be reduced by 1 dose level.
 
If QTcF remains ≥ 481 ms after performing steps 1-4 as directed in "For All Grades," discontinue LEE011.
 
Repeat ECGs 7 days and 14 days after dose resumption (then as clinically indicated) for any patients who had therapy interrupted due to QTcF ≥ 501 ms.
 
If QTcF of ≥ 501 ms recurs, discontinue ribociclib.

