7.2.2.5 Cardiac assessments

7.2.2.5.1 Electrocardiogram (ECG)

A standard 12-lead ECG will be performed after the patient has been resting for 5-10 min prior to each time point indicated in [Table 7-4](#) below. Tracings must be dated and signed by the investigator (or his/her designee) and filed with the patient's source documentation. QTc intervals should be calculated according to Fridericia. Each ECG tracing should be labeled with the study number, patient number, date, and kept in the source documents at the study site. Clinically significant ECG abnormalities present at screening when the patient signed informed consent should be reported on the Medical History eCRF page. New or worsened clinically significant findings occurring after informed consent must be recorded on the Adverse Events eCRF page ECG may be repeated at the discretion of the investigator at any time during the study and as clinically indicated; any clinically relevant findings should be added to the Adverse Events eCRF.

Table 7-4 ECG collection plan

Cycle	Patients	Day	Time
Screening	All	-7 to -1	Anytime
1	All	Day 15	Anytime
2	All	Day 1	Anytime
	All	Day 15	Anytime
3-6	All	Day 1	Anytime
All other cycles	Patients with QTcF \geq 481 ms at any time prior to cycle 7	Day 1	Anytime
EOT		Anytime	
Unscheduled ECG			Anytime

If any of the readings include an abnormal ECG or an average QTcF value of \geq 481 ms is obtained at any time after enrollment in the study, treatment must be interrupted, repeat ECG and follow management guidelines detailed in Table 6-5.

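### Section 6.3.4 interrupts ribociclib for an unavoidable known-TdP-risk drug but ties no ECG or QTcF check to restarting it

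*Protocol*

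**What the plan says.** Sections 6.3.3 and 6.3.4 prohibit drugs with a known risk of QT prolongation or torsades during study treatment. Section 6.3.4 adds a fallback for when one is unavoidable: "If concomitant administration of drugs with a known risk of TdP is required and cannot be avoided, LEE011/placebo must be interrupted". (LEE011 is ribociclib; this trial has no placebo.) For drugs of possible or conditional risk, the same section says that "study treatment may be resumed under close clinical and ECG monitoring to ensure patient safety".

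The related rules elsewhere in the protocol are these:

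- **Entry (5.3, criterion 16).** A patient is excluded if taking a QT-prolonging drug "that cannot be discontinued (within 5 half-lives or 7 days prior to starting study drug) or replaced by safe alternative medication".
- **QTcF-driven interruptions (6.2.1.3, Table 6-5).** The table says: "Repeat ECGs 7 days and 14 days after dose resumption (then as clinically indicated) for any patients who had therapy interrupted due to QTcF" at or above the stated thresholds. Restart needs QTcF below 481 ms.
- **Scheduled ECGs (7.2.2.5.1, Table 7-4).** All patients have ECGs at screening, on Day 15 of cycle 1, on Days 1 and 15 of cycle 2, and on Day 1 of cycles 3 to 6. Later cycles have a Day 1 ECG only for patients who reached 481 ms before cycle 7. There is one more ECG at end of treatment.
- **Other ECGs (7.2.2.5.1).** "ECG may be repeated at the discretion of the investigator at any time during the study and as clinically indicated".
- **Biochemistry (7.2.2.4.2).** Tests are scheduled on Day 1 of each cycle, with extra Day 15 tests in cycles 1 and 2. The panel includes potassium, calcium and magnesium.
- **Interruptions (6.6).** More than 4 weeks off ribociclib ends study treatment. Weekly follow-up applies when the cause is an adverse event or abnormal laboratory value. Use of prohibited medication is listed as a reason for which a patient may be withdrawn.

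**The concern.** The rule in 6.3.4 ends at the interruption. A patient who has finished the known-risk drug can go back on ribociclib the next day, at full dose, without an ECG, and the protocol has been followed.

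This matters because both drugs prolong QT. The Amendment 4 rationale says that ribociclib's effect rises with its concentration. Section 1.2.1.2.1 says that QT changes "are associated with the maximum drug levels between 1 to 8 h post-dose". A restart therefore brings back ribociclib peaks on the first day, when the other drug may still be present. There is a smaller overlap at the other end, because ribociclib is still in the body when the known-risk drug starts.

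The exception is foreseeable. Table 14-1 lists common antibiotics, ondansetron, propofol and sevoflurane as known-risk drugs. At stake is the safety of individual patients. No estimate in the analysis plan depends on this.

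**Working it through.** **1. Is there a required ECG or QTcF check at restart?** Each rule that might supply one is set against this situation.

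| Rule | Applies when | Covers restart after a known-risk drug? |
|---|---|---|
| 5.3, criterion 16, washout | before first study dose | no |
| Table 6-5, QTcF below 481 ms and ECGs at 7 and 14 days | interruption caused by QTcF | no |
| 6.6, weekly follow-up | interruption for an adverse event or abnormal laboratory value | only if an adverse event also caused the interruption; no ECG named |
| 6.6, withdrawal | use of prohibited medication | optional; not a restart rule |
| 6.6, 4-week limit | any interruption | sets a maximum; not a restart rule |
| Table 7-4, cycles 1 to 6 | fixed days | only if restart falls on an ECG day |
| Table 7-4, cycle 7 onward | earlier QTcF of 481 ms or more | not for other patients |
| 7.2.2.5.1, extra ECGs | investigator's discretion | permitted, not required |
| Day 1 biochemistry | each cycle | electrolytes only, and only if restart falls on Day 1 |

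Take a patient in cycle 8 with no earlier QTcF of 481 ms who needs levofloxacin (Table 14-1) on ribociclib dosing days. Ribociclib stops, the course ends, and ribociclib restarts mid-cycle. The protocol schedules no ECG at any of these steps.

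**2. How fast does ribociclib clear?** Inputs are the accumulation ratio (Racc) and the effective half-life derived from it. They come from section 1.2.1.2.3 (single agent) and from section 1.2.6 with Table 1-3 (600 mg plus letrozole).

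Formula, with a 24 h dosing interval: T1/2,acc = 24 × ln 2 / ln[Racc / (Racc − 1)].

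- Racc 1.35 gives 12.3 h and Racc 3.11 gives 42.9 h. These reproduce the protocol's own range, which "ranged from 12.3 to 42.9" (unit not printed, so hours).
- Racc 2.4 gives 30.9 h, against a stated mean of 32.5 h. The 5% difference is expected, because the table averages patient-level values from 19 and 18 patients.

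Five half-lives at 32.5 h is 5 × 32.5 / 24 = 6.8 days. One SD either side (32.5 ± 12.5, so 20 to 45 h) gives 4.2 to 9.4 days. After 7 days off, 2^(−168/32.5) = 2.8% remains, or 6.6% at 42.9 h. A 7-day look-back is therefore a sensible window for asking whether ribociclib is still present when the known-risk drug starts.

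These figures assume linear kinetics. Section 1.2.6 gives a reason for caution: "Ribociclib accumulated 2.4-fold following multiple doses, possibly due to a combined effect of drug accumulation and auto-inhibition of CYP3A4".

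**3. How high is the first peak after restart?** Table 1-3 gives mean Cmax of 1130 ng/mL on cycle 1 Day 1 (n = 41) and 1870 ng/mL on Day 21 (n = 28).

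1130 / 1870 = 60%.

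This takes cycle 1 Day 1 as a stand-in for the first 600 mg dose after a long interruption. After a short one, residual drug would add to it. Tmax in Table 1-3 is about 2 h, so the peak comes the same day.

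**4. ECG count for the fix.** Restart, day 7 and day 14 make 3. One more around the first dose of the known-risk drug makes 3 + 1 = 4.

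**The case against.** **Interruption is already the stricter control.** A reader might infer that the highest-risk class has a weaker rule than the possible- and conditional-risk classes, because only the latter carry an ECG requirement. The documents do not support that. For known-risk drugs one of the two QT-prolonging agents must be removed. ECG monitoring is attached where both may be given together. The gap lies at the edges of the interruption, mainly at the restart.

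**Other provisions help.** Many unavoidable uses would treat an adverse event, and Table 6-6 then holds ribociclib until recovery from grade 2 or 3 events. Section 6.2.1.4 suggests considering electrolyte tests and holds ribociclib while they are abnormal. Patients must report new medications (6.3.1), and the medical monitor is available for questions (6.3.3). This stands as partial cover. None of it requires an ECG, and it misses elective uses such as anaesthesia.

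**The size is not known.** The documents give no rate of unavoidable use and no figure that converts ribociclib exposure into QTcF for this overlap. This stands in full.

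**A single exposure percentage would be tempting.** From Racc 2.4 a reader might compute 1 − 1/2.4 = 58% of daily exposure remaining on the first missed day, and take that as the risk. It does not bear that weight. It is a share of AUC, while section 1.2.1.2.1 ties QT change to maximum levels. It runs from 38% to 69% over Racc ± 1 SD, and it assumes linear kinetics. It also conflicts with a simple decay fitted to the same table. Mean level over Cmax is 25900/24/1870 = 57.7%, which under a single exponential leaves 29% of peak at 24 h. But 0.583 × 0.577 requires at least 34%.

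**Conclusion.** The point holds as a gap in a safety procedure. After an interruption for a known-risk drug, the protocol requires no ECG or QTcF value before ribociclib restarts. The gap is widest from cycle 7, when patients without an earlier QTcF of 481 ms or more have no scheduled on-treatment ECG. Through cycle 6 it is narrower but still there, because the scheduled ECGs follow the calendar and not the co-medication.

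The pharmacology supports two modest statements. Ribociclib takes days to clear (mean effective half-life 32.5 h, wide spread, possibly inflated by auto-inhibition). The first dose back reaches roughly 60% of the steady-state peak, if cycle 1 Day 1 is a fair stand-in. Neither gives a number of patients or events, and none is claimed.

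A reader might go further and infer that the protocol allows ribociclib alongside a known-risk drug. It does not: the prohibition in 6.3.3 and 6.3.4 bars restart while that drug is still being given. The clinical benefit rate analysis is not touched. This is a cheap improvement, worth making for patients still on treatment.

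**What to change.** Add one paragraph to 6.3.4 by written amendment (section 12.1):

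1. After an interruption for a known-risk drug, ribociclib restarts only once that drug has been stopped, an ECG shows QTcF below 481 ms, and electrolytes are in the normal range.
2. ECGs are repeated 7 and 14 days after restart, as Table 6-5 already does.
3. If ribociclib was taken in the previous 7 days, an ECG is also obtained around the first dose of the known-risk drug, where feasible.
4. The length of any washout stays with the investigator.

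Item 4 is deliberate. A mandatory 7-day washout would count toward the 4-week limit and cut the longest course that fits from 28 to 28 − 7 = 21 days. A strict five half-lives would exceed the limit after a 7-day course for any drug with a half-life above (28 − 7)/5 = 4.2 days, and so force permanent discontinuation. After a single dose of an anaesthetic or anti-emetic, either rule would be out of proportion.

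The cost is about 3 to 4 local ECGs per episode, an electrolyte panel when restart does not fall on Day 1, and possibly a short delay. A scheduled ECG or Day 1 panel can serve as the restart check if done before the dose. Enrollment was complete at Amendment 4, so only patients still on treatment benefit.
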